10.0 Procedures Involved

10.1 Describe and explain the study design.

Once a subject has been identified, the initial visit will be scheduled. During the experimental day, informed consent will be completed, and the subjects will complete the following tasks: (1) an investigator will conduct visual acuity assessments of both eyes (Snellen). (2) The subjects will be asked to complete a survey (on contact lens satisfaction). (3) After the survey, the subject will sit with their lenses for assessment using the Keratograph topographer. (4) After topography, slit lamp assessment of the rigid lenses, and then of the cornea and conjunctiva (after lens removal) with and without Lissamine Green staining will be done.

At visit one, the following additional task will be performed: (1) The subject will be asked to sit for a corneal or scleral lens fitting visit (based on what they wear habitually), where the investigator will fit the subject with a commercially available scleral or corneal lens. All subjects will be refit into the Advanced Vision Technologies (AVT) brand of rigid lenses, manufactured at AVT Technologies in Colorado. If they already wear the AVT brand, the lens parameters will simply be re-ordered. All lenses will undergo a diagnostic fit with an AVT lens. The parameters available at AVT are similar to those available at all other major labs in the US.

A second visit will be to evaluate the fit of the ordered study lenses (which will have been coated with the HydraPEG coating), and will be for the dispense of the lenses. In addition to evaluating the lenses, the subjects will be asked to complete a short survey on their satisfaction with their current lenses. After this visit, the subjects will then wear the lenses for 30 days, on a daily basis as they habitually would, cleaning the lenses with ClearCare hydrogen peroxide cleaning system, a commonly used commercially available soft and rigid contact lens cleaner. After 30 days of lens wear, they will report for visit 3.

At the third visit, the same testing will be performed from visits 1 and 2, the subject will also be given an additional survey regarding the satisfaction with the HydraPEG lenses, and then the Tangible Boost kit or the placebo kit (consisting of

Page 9 of 22 Revised: July 24, 2017

two vials with Unique pH) solutions will be dispensed (randomized) to store their lenses in for 30 minutes that night.

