The solution will be dispensed and the subjects trained on its use, and the subjects will be asked to store their lenses in the given solution for 30 minutes that evening, and then transfer their lenses to Unique pH multipurpose rigid lens solution for overnight storage. For the initial training with the Boost or placebo system, the users will undergo an approximately 60-minute user training in which there will be visual and audio recording and still photographs taken in order for a human factors company (Userwise) to analyze the usability of the product. The investigator at the study visit will act as the monitor for the training session. This recorded training step was specifically designed to allow for proper evaluation of the usability of the product, which they will report to the FDA to ensure usability. At the initial visit, the subject will have indicated on the informed consent form whether they agree to participate in the recorded portion of the training. If they do not participate in the recording, they can still be trained and participate in the study.

The subjects will report to the Ocular Surface Institute the next day for Visit 4, at which time the comfort and visit tests will occur again, and an additional survey to evaluate the boost treatment will be given. After visit 4, the subjects will continue to wear the study lenses daily for an additional 60 days, treating their lenses again in the Boost or placebo solution at the midpoint between visit 4 and 5 (30 days after the first treatment with Boost), otherwise cleaning nightly with ClearCare, and will then report to the clinic again 30 days after the midway treatment (approximately 90 days after the initial HydraPEG dispense). The same visit testing will be done at this final and 5th visit, and a final short survey will be done, and then the lenses will be collected from the subjects and sent back to Tangible Science, Inc. for their internal testing of the lenses (no involvement of the UH research team). At this time the study will conclude.

The following table outlines each of the study visits and tells what procedures will be done at each visit:

Procedure	Length of Time Required for	Frequency of Repetition
VISIT 1: Initial Evaluation		
Informed consent & HIPAA	35 minutes	Once
General History and medications	5 minutes	Once per visit
Visual Acuity	5 minutes	Once per visit

Page 10 of 22 Revised: July 24, 2017

Questionnaires (CLDEQ8 + VAS)	10 minutes	Once per visit

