Keratograph Surface Evaluation	5 minutes	Once per visit
Slit-lamp Examination (with lenses	10 minutes	Once per visit
on and after lens removal)		
Scleral lens / corneal lens fitting	30 minutes	Once
	100	
TOTAL TIME	100 minutes	
VISIT 2: HydraPEG dispense		
Visual Acuity	5 minutes	Once per visit
Questionnaires (CLDEQ8 + VAS	10 minutes	Once per visit
+ Secondary VAS for V2)		Shee per visit
, , , , , , , , , , , , , , , , , , ,		
Keratograph Surface Evaluation	5 minutes	Once per visit
Slit-lamp Examination	5 minutes	Once per visit
Scleral/corneal lens evaluation &	20 minutes	Once
dispense. (handling & care		
paperwork will be dispensed at this		
visit)		
TOTAL TIME		
*additional visits may be required to		
not acceptable. It is anticipated that		
Visit 1 and 2). The only tasks done		
of the lens and make any necessary of		
minutes – for a slit lamp evaluation		
determined. Since these are establish	ned wearers, we do not antici	pate a long fitting process.
VISIT 3: Tangible Boost Dispense		T
Visual Acuity	5 minutes	Once per visit
Questionnaires (CLDEQ8 + VAS	10 minutes	Once per visit
+ Secondary VAS for V3)		
Keratograph Surface Evaluation	5 minutes	Once per visit
Slit-lamp Examination	5 minutes	Once per visit
Tangible Boost kit dispense &	60 minutes	Once
training		
TOTAL TIME	85 minutes	
VISIT 4: Tangible Boost Follow-U	p #1	
Visual Acuity	5 minutes	Once per visit
Questionnaires (CLDEQ8 + VAS	10 minutes	Once per visit
+ Secondary VAS for V4)		
Keratograph Surface Evaluation	5 minutes	Once per visit
Keratograph Surface Evaluation Slit-lamp Examination	5 minutes 5 minutes	Once per visit Once per visit

Page 11 of 22 Revised: July 24, 2017

FULL PROTOCOL TITLE: An Evaluation of Tangible Boost Replenishing System on the Continued Efficacy of Tangible HydraPEG Rigid Gas Permeable Contact Lens Coating.

TOTAL TIME	25 minutes	
VISIT 5		
Visual Acuity	5 minutes	Once per visit
Questionnaires (CLDEQ8 + VAS + Secondary VAS for V5)	10 minutes	Once per visit
Keratograph Surface Evaluation	5 minutes	Once per visit
Slit-lamp Examination	5 minutes	Once per visit
TOTAL TIME	25 minutes	

10.2 Provide a description of all research procedures being performed and when they are performed.

The testing descriptions are summarized in the table below:

Test	Description	Video/Audio recording
General History and Medications	Participants will be asked questions about their general, ocular and medication use histories along with contact lens use history if applicable.	No

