Questionnaires	Subjects will be asked to fill out the following questionnaires: • Contact Lens Dry Eye Questionnaire - 8 (CLDEQ - 8) • Visual analog scale (VAS) 0-100 • Secondary VAS scales at Visits 2-5 (unique to each visit) These questionnaires assess the level of eye and/or contact lens discomfort, and assess the subject perception of their habitual lenses and the coated lenses before and after Boost treatment.	No

Page 12 of 22 Revised: July 24, 2017

FULL PROTOCOL TITLE: An Evaluation of Tangible Boost Replenishing System on the Continued Efficacy of Tangible HydraPEG Rigid Gas Permeable Contact Lens Coating.

0.1.1/0.1	TT1 ' '11 ("1 1 1 1 1 1 1	NT
Scleral/Corneal lens fitting	The examiner will fit the subjects with scleral or corneal contact lenses using commercially available lens fitting sets (AVT scleral and corneal designs, AVT Technologies, CO). The lenses will be fit using the customary fitting procedure, where a diagnostic lens is applied to the eye, an over-refraction is performed, and then customized lenses are ordered with the over-refraction incorporated and any fitting parameters are altered based on the investigators' expertise. Once the lenses are dispensed, the subjects will be reminded of proper handling and cleaning techniques, and given a handout on lens care. In addition, at the 30-day visit subjects will be given instructions on the tangible boost kit or placebo that they are supplied.	No
Scleral/Corneal	The ordered rigid lenses will be applied to the eye of the	No
Lens Evaluation	subject by the investigator, after which the fit and vision will be evaluated. At this time, if the fit of the lens is adequate, the lenses will be dispensed. If there are additional parameter changes needed, they will be ordered at this time.	
Visual Acuity	The participant's vision in each eye will be measured with a high contrast visual acuity chart for the subjects' habitual lenses and the test lenses. The participant will be asked to cover one eye and read the chart, and this procedure will be repeated for the other eye.	No
Slit-lamp	The participant's front portion of each eye and contact	No
Examination	lenses will be examined with a lighted microscope. The participant will be asked to place his/her chin on the chinrest and place his/her forehead against the bar and look straight ahead. The instruments light will be shined onto the eye to visualize the ocular surface for approximately 2-3 minutes per eye.	

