30.0 Additional Approvals

• N/A

Page 22 of 22 Revised: July 24, 2017

After giving the potential subject an overview of their role in the study, the investigator will ask:

Q1. Do you wear rigid contact len yes, continue to Q2)	Do you wear rigid contact lenses as your primary mode of vision correction? (if			
yes, continue to Q2)	Yes	No		
Q2. Do you have any eye conditio	ns that you know of?			
If yes, name them:	Yes	No		

note: patients will probably name the condition that they are being prescribed rigid lenses to treat. These conditions are allowed; exclusions are only if the patient has other ocular disease that could confound the data.

Q3: Do you have any allergies to eye drops that you are aware of? Additionally, do you know of any allergies you have to the following substances: Dextran, polyethylene glycol, hydroxypropyl methylcellulose, or polyvinyl alcohol?

Yes No

If no to both parts, continue to Q4.

Q4: As far as you know, are you allergic to Unique pH multipurpose GP lens cleaner?

Yes

No

If no, they qualify for the study.

At this point, if the patient is still interested in participating in the study, the investigator can begin the formal Informed Consent process.

Instructions for Contact lens Handling:

- Clean lenses with **Unique pH**
- Store lenses in **Unique pH**
- Rinse lenses (if needed) with **Purilens or Unique pH**
- Do not use tap water on lenses

Patient ID:	
Date:	
Visit #:	
Please rate on the scale below how comfortable your hab	itual lenses are upon insertion on an average day ?
ı	I
extremely uncomfortable	extremely comfortable
Please rate on the scale below how comfortable your hab	itual lenses are at the end of the day on an average
extremely uncomfortable	extremely comfortable
Please rate on the scale below what the quality of your vi	sion is on an average day with your habitual lenses?
Poor vision, unable to	Excellent vision, no
function	awareness of blue
On average, how many hours each day can you comfortal	oly wear your habitual lenses?

Patient Survey: Boost Dispense Visit
Patient ID:
Date:
Visit #:
Please rate on the scale below how comfortable the Hydra-PEG study lenses are upon insertion on an average day?
extremely uncomfortable extremely comfortable
Please rate on the scale below how comfortable the Hydra-PEG study lenses are at the end of the day on an average day ?
extremely uncomfortable extremely comfortable

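### Section 10.1 prescribes ClearCare for routine cleaning while the lens-handling sheet prescribes Unique pH, so the care regimen, the meaning of the placebo and any Visit 3 to Visit 4 within-subject change are left unsettled

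*Combined protocol and SAP*

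**What the plan says.** Section 10.1 describes three periods.

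- Visit 2 to Visit 3 (30 days): daily wear, "cleaning the lenses with ClearCare hydrogen peroxide cleaning system".
- The evening of Visit 3: a 30-minute soak in Boost or placebo, after which subjects "transfer their lenses to Unique pH multipurpose rigid lens solution for overnight storage". Visit 4 is the next day. The placebo kit is itself two vials of Unique pH.
- Visit 4 to Visit 5 (60 days): one further soak at the midpoint, "otherwise cleaning nightly with ClearCare".

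The lens-handling sheet, among the forms after section 30.0, says "Clean lenses with Unique pH" and "Store lenses in Unique pH". It does not mention ClearCare. Section 10.2 says that at dispensing "the subjects will be reminded of proper handling and cleaning techniques, and given a handout on lens care", and the 10.1 visit table places the handling and care paperwork at Visit 2.

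The Visit 2, 3 and 4 worksheets each have an item for dispensing Unique pH and none for ClearCare. In the screening questions, Unique pH is the only care solution named. The Visit 2 to 5 worksheets have a free entry for the cleaning solution in use.

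On analysis, the statistical paragraph in 10.2 makes each subject their own control, with paired non-parametric tests of pre/post differences. It treats with-versus-without Boost descriptively. Section 25.1 lists families of tests and models for baseline against test data. Neither names the visits to be compared or a between-arm comparison.

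**The concern.** Section 1.1 gives cleaning, along with blinking, as a reason the coating wears off. The routine care system may therefore affect how much coating is left at Visit 3 for Boost to restore. Two regimens are prescribed and a subject can follow only one.

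The conflict also changes what the control is. Under the handling sheet, the placebo is another 30 minutes in the solution used every night. Under 10.1, it is a solution outside routine care.

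Finally, it matters for a before/after reading of Boost. Visit 3 and Visit 4 sit on either side of the first soak and are a natural pre/post pair. If the overnight solution also changes between them, their difference cannot be credited to the soak alone.

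**Working it through.** **Extent of the conflict.** The intervals are 30, 1 and 60 days, from 10.1 and the scheduling items on the Visit 2 and Visit 4 worksheets. Total nights = 30 + 1 + 60 = 91.

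| Interval | Nights | Section 10.1 | Handling sheet |
|---|---|---|---|
| Visit 2 to 3 | 30 | ClearCare | Unique pH |
| Visit 3 to 4 | 1 | soak, then Unique pH | soak, then Unique pH |
| Visit 4 to 5, ordinary nights | 59 | ClearCare | Unique pH |
| Visit 4 to 5, midpoint soak | 1 | soak, then Unique pH (assumed) | soak, then Unique pH (assumed) |

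Under 10.1, ClearCare nights = 30 + 59 = 89 and Unique pH nights = 91 − 89 = 2. Under the sheet, Unique pH is used on all 91. The assumption is that the midpoint soak night ends as the first one does; 10.1 does not say. This count measures the disagreement between the texts, not an effect on any endpoint.

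**Which comparisons are affected.** For the change from Visit 3 to Visit 4, let b be the effect of the Boost soak, p that of the placebo soak, s that of changing the overnight solution, and c any other shift common to both arms (time, retest, training).

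- Boost arm, within subject: b + s + c.
- Placebo arm, within subject: p + s + c.
- Difference between arms: (b + s + c) − (p + s + c) = b − p.

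If only fractions q_B and q_P of the two arms experience the switch, the difference is b − p + s(q_B − q_P). Mixed use therefore does no harm on average unless it depends on arm.

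Under the handling sheet s = 0. From Visit 3 to Visit 5 under 10.1, routine care is ClearCare before both visits, so again there is no switch.

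Taking s as non-zero under 10.1 requires ClearCare to be the overnight system before Visit 3. For that period 10.1 says cleaning and names no storage solution; overnight use is inferred from the nightly wording for Visits 4 to 5.

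**What the between-arm test costs in power.** Inputs: 15 per arm (the 30 completers in section 5.2, with 1:1 allocation assumed); normal changes with SD 1; p = c = 0; two-sided 5%; 100,000 simulated trials. The exact signed-rank test (reject at W ≤ 25, size 0.0479) is applied within the Boost arm, and the exact rank-sum test (reject at U ≤ 64, size 0.0453) between arms.

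| True Boost effect, no switch effect | Paired, Boost arm | Between arms |
|---|---|---|
| 0.5 SD | 0.416 | 0.24 |
| 0.8 SD | 0.802 | 0.525 |

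**Illustration only.** The documents give no value for s. If Boost adds nothing and s is 0, ±0.2 or ±0.5 SD, the paired test rejects about 5%, 11% or 41% of the time, in whichever direction s points. The between-arm test rejects 4.5% of the time throughout. Any common shift c of the same size would give the same rates, so these figures do not estimate bias in this trial.

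**The case against.** The strongest reply is that this is a wording slip with no demonstrated consequence. The handling sheet and the dispensing items point to Unique pH, so the two ClearCare sentences may simply be out of date; in that case there is no switch. No section names Visit 3 to Visit 4 as the paired contrast, and baseline could equally mean the habitual lenses at Visit 1. CLDEQ-8 asks about the past week, so at Visit 4 it mostly covers days before the soak. The absence of a named between-arm test is a separate weakness, present whatever the care solution.

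Most of this stands. It limits the consequence but does not remove the contradiction, because the visible text does not say which regimen governs. The worksheets do not settle it either. Unique pH at Visit 2 could be advance supply or for rinsing, and the Unique pH items at Visits 3 and 4 and in screening fit either regimen. Treating the sheet as the handout given at dispensing is reasonable but inferred. The kit instructions, dispense log and consent form are not in the text reviewed. The cleaning-solution entries show afterwards what was used, not what was prescribed.

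A reader might infer that the switch biases the trial's result for Boost, or that the randomised comparison is confounded. The documents do not support either reading. The switch is common to both arms and cancels between them, its size and direction are unknown, and it exists only if 10.1 is followed with ClearCare overnight.

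**Conclusion.** The contradiction is certain: 10.1 and the handling sheet prescribe different routine care on about 89 of 91 nights, and they give the placebo different meanings. It should be resolved before lenses are dispensed.

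The analytical consequence is conditional. It requires that 10.1 is what happens, that ClearCare is the overnight system before Visit 3, and that a Visit 3 to Visit 4 within-subject change is used to judge Boost. That change would then mix the soak with a change of overnight solution, by an amount and in a direction the documents do not allow anyone to state. The between-arm contrast is sound as long as regimen use does not depend on arm.

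**What to change.** Before dispensing, name one routine care system in 10.1, the handling sheet, the screening question and the dispensing items, and use the same overnight solution on the nights before Visits 3 and 4. The sponsor and investigator decide which product is right.

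- **If Unique pH is intended:** change the two ClearCare sentences in 10.1. The overnight solution is then the same before both visits.
- **If ClearCare is intended:** correct the handling sheet, add ClearCare to the screening allergy question, and add a ClearCare dispensing item to the Visit 2, 3 and 4 worksheets. Keep the Unique pH items, since it remains the placebo and post-soak solution. Because that leaves the switch in place, either align the overnight solution before Visit 3 with the post-soak solution (one more sentence in 10.1) or rely only on the between-arm contrast at Visit 4.

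Either way, add one sentence basing the conclusion about Boost on the between-arm difference in change from Visit 3 to Visit 4 and to Visit 5, with a confidence interval. Add another to tabulate the recorded cleaning solution by arm at Visits 3, 4 and 5, which would show any imbalance in use.

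No new data are needed beyond these form changes. The real cost is the lower power shown above, in return for a comparison that separates Boost from the switch.

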1.0 Objectives

1.1 Describe the purpose, specific aims, and/or objectives.

The goal of this research is to determine if the Tangible Boost system adequately replenishes the HydraPEG coating on the surface of a rigid contact lens. HydraPEG is a soft and rigid contact lens coating, primarily composed of polyethylene glycol, which is covalently bound to the surface of a contact lens. The HydraPEG coating is intended to improve wettability and comfort with rigid lenses, and is currently FDA approved. HydraPEG can be applied to soft or rigid contact lenses, but the coating naturally diminishes from the surface of the lens over time (due to cleaning, and blinking over the surface of the contact lens). Tangible Science, the company that produces HydraPEG, has recently come out with a new product called Tangible Boost, intended to be used every 30 days and replenish the coating on the surface of the lens.

Tangible Boost (also known as HydraPEG Replenish in some of the FDA documents) is a solution composed on the same components of the HydraPEG coating). Essentially, Tangible Boost solution is the HydraPEG coating, it is just in solution that can be used at home by the subjects after the initial HydraPEG is applied at the lens manufacturing lab. The Tangible Boost kit consists of two unit dose HydraPEG solutions (components A and B), as well as a barrel case, and the lens wearers are instructed to empty the two vials into the case and soak their lenses for 30 minutes every 30 days to replenish the coating. This product configuration has been optimized to facilitate ease of use for the patient.

This is a study to evaluate the efficacy of Tangible boost to replenish the HydraPEG coating on rigid gas permeable (scleral and corneal) contact lenses.

1.2 State the hypotheses to be tested.

We hypothesize that the Tangible Boost replenishing system will re-build the HydraPEG coating that naturally diminished from the contact lens surface over time, and improve the comfort and visual performance of HydraPEG coated rigid gas permeable lenses. We anticipate that this be shown by improved patient symptoms and lens wettability after treatment with Tangible Boost.

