24.0 FERPA - N/A

25.0 Data Management

25.1 Describe the data analysis plan, including any statistical procedures.

Data will be stored in a study paper file. Paper files will be kept in a filing cabinet within The Ocular Surface Institute (Health and Biomedical Sciences Building). Electronic data will be stored on a password-protected computer in a locked office in rooms 232, 236 or 250 within The Ocular Surface Institute of the Health Biological Sciences Building (HBSB). All study data will remain on UH property within The Ocular Surface Institute for a minimum of 3 years following study completion. The principal investigator will be

Page 20 of 22 Revised: July 24, 2017

responsible for maintaining study data security and subject confidentiality, and the PI and the study coordinator will be responsible for receipt and transmission of the data. The investigative team, study sponsor and inspectors from regulatory agencies such as the US Food and Drug Administration will have access to the data if requested for study monitoring or an audit.

All collected data will be documented on study documents and analyzed for differences between baseline and test data. Hypothesis testing will be performed using statistical analyses including parametric or nonparametric comparisons (i.e., t-tests, signed-rank tests), analysis of variance, general linear models, correlation, or regression techniques.

The recorded audio and video data will be sent to UserWise for analysis of the usability of the product.

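### In the Boost arm, Visits 3 and 5 both fall about 30 days after the last coating, so a paired Visit 3-to-5 comparison could miss an effective product; Visit 5 needs a Boost-versus-placebo contrast

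*Combined protocol and SAP*

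**What the plan says.** Section 1.1 describes a coating that wears away with cleaning and blinking, and a kit meant to replenish it every 30 days. Section 1.2 gives the expected result: "We anticipate that this be shown by improved patient symptoms and lens wettability after treatment with Tangible Boost". It names no visit and no comparator.

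Section 10.1 sets the schedule. Coated lenses are dispensed at Visit 2. "After 30 days of lens wear, they will report for visit 3". At Visit 3 the kits are randomized: "two vials with Unique pH) solutions will be dispensed (randomized) to store their lenses in for 30 minutes that night". "The subjects will report to the Ocular Surface Institute the next day for Visit 4". The second soak comes "at the midpoint between visit 4 and 5 (30 days after the first treatment with Boost", and subjects "will then report to the clinic again 30 days after the midway treatment (approximately 90 days after the initial HydraPEG dispense".

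On analysis, the statistical paragraph of 10.2 treats each subject as their own control, with paired non-parametric pre/post tests, and adds descriptive statistics with and without Boost. Section 25.1 says the data will be "analyzed for differences between baseline and test data" and lists candidate methods, from t-tests and signed-rank tests to analysis of variance and general linear models. Neither section says which visits form the contrast, and neither specifies a test of Boost against placebo.

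**The concern.** A pre/post comparison shows replenishment only if the two readings fall at different points of the coating cycle. Visit 3 is the last reading before treatment, and so the natural pre value. Visit 5 is the final reading and the only one after sustained use. In the Boost arm both fall at the end of a 30-day cycle. If Boost does what 1.1 describes, the lens should be in much the same state at both.

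A working product could then be reported as showing no improvement at the final visit, and a partly working one as getting worse. What Visit 5 can show is that Boost lenses hold up while placebo lenses go on losing coating. That is a between-arm result, which the paired analysis does not deliver.

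**Working it through.** **Day count, from the intervals in 10.1.** Dispense is day 0. Visit 3 and the first soak (that evening) are day 30, and Visit 4 is day 31. The second soak is day 30 + 30 = 60, and Visit 5 is day 60 + 30 = 90. This reproduces the protocol's figure of about 90 days. Counting Visit 5 as Visit 4 plus 60 days gives day 91, whose midpoint with Visit 4 is day 61; the one-day difference is immaterial.

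Days since the last active coating:

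| Visit | Study day | Boost | Placebo |
|---|---|---|---|
| 3 (before soak) | 30 | 30 | 30 |
| 4 | 31 | 1 | 31 |
| 5 | 90 (91) | 30 (30 or 31) | 90 (91) |

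**Expected change under an assumed model.** The documents give no loss rate, so this is illustration. Let a full coating be 1.0 and r the share kept per 30 days, with exponential loss, C(t) = r^(t/30). Placebo restores nothing. A soak applied at level x gives x + f(1 - x), where f is the share of the lost coating restored.

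- Visit 3, both arms: r.
- Visit 5, Boost with f = 1: back to 1.0, then r. The change from Visit 3 is r - r = 0 for every r.
- Visit 5, placebo: r^3. The change is r^3 - r.
- Visit 5, Boost with f = 0.5 and r = 0.5: 0.5 → 0.75 → 0.375 → 0.6875 → 0.344, a change of -0.156.

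| Loss per 30 days | Visit 3 | Boost change, f = 1 | Boost change, f = 0.5 | Placebo change | Boost minus placebo, f = 1 | Boost minus placebo, f = 0.5 |
|---|---|---|---|---|---|---|
| 20% | 0.800 | 0 | 0.688 - 0.800 = -0.112 | 0.512 - 0.800 = -0.288 | +0.288 | +0.176 |
| 50% | 0.500 | 0 | 0.344 - 0.500 = -0.156 | 0.125 - 0.500 = -0.375 | +0.375 | +0.219 |
| 80% | 0.200 | 0 | 0.112 - 0.200 = -0.088 | 0.008 - 0.200 = -0.192 | +0.192 | +0.104 |

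The within-arm change is zero or negative throughout, while the between-arm difference is positive throughout, even with half restoration. From Visit 3 to Visit 4, with f = 1 and 50% loss, the Boost arm gains 0.977 - 0.500 = +0.477.

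**What the tests would show.** In 4,000 simulated trials I assumed 15 subjects per arm (the protocol analyses 30 completers and gives no allocation ratio), normal changes with SD 1, and two-sided 5% tests. With a true Boost-arm change of zero, a signed-rank test of Visit 3 to 5 finds significant improvement about 2% of the time, which is the false-positive rate in that direction. A Mann-Whitney test of the change between arms has about 23%, 52% and 73% power when placebo loses 0.5, 0.8 and 1.0 SD.

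**Which measures can use Visit 4.** Break-up time, acuity and the momentary comfort VAS can respond within a day. The CLDEQ-8 asks about the past week, so at Visit 4 it covers almost only wear before the soak. The Visit 4 survey has no item on end-of-day comfort or comfortable wearing hours, although the Visit 4 worksheet keeps a space for a removal score. The surveys for Visits 3 and 5 ask both. For these symptom measures, Visit 5 is in practice the only post-Boost reading.

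**Other meanings of baseline.** If it means Visit 1, a gain mixes new coated lenses against habitual ones with any Boost effect. If it means fresh lenses at Visit 2, Visit 5 is expected to be lower (1.0 against r).

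**The case against.** A reader might infer that the protocol states a Visit 5 hypothesis in the wrong direction, so that a fully effective Boost must fail. The documents do not support this. Section 1.2 predicts improvement after treatment without naming a visit, and the analysis text names none either. Visit 4, one day after the first soak, gives improvement a fair chance on several measures, so the hypothesis is testable there. Maintenance is not foreign to the protocol: the title concerns the coating's continuing efficacy, and 2.1 presents Boost as part of maintaining the surface treatment. Methods listed in 25.1 could carry a between-arm comparison.

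Zero change is also a model result. It requires that a soak restores no more than the as-dispensed level and that wear is unchanged. If each soak added 1.0 without a cap, at 50% loss per 30 days, the path would be 0.5 → 1.5 → 0.75 → 1.75 → 0.875, an improvement of 0.375. The documents give no ceiling, and no link between the amount of coating and symptoms or break-up time.

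All of this stands and limits the claim. It does not remove the matched timing in the Boost arm, or the lack of a specified contrast that would make Visit 5 informative.

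**Conclusion.** The point holds as a design and wording gap that should be closed. The matched timing in the Boost arm (about 30 days at both visits, against about 90 for placebo at Visit 5) follows from the protocol's own intervals. That the within-arm Visit 3-to-5 change is about zero, or negative with partial restoration, rests on the assumption of restoration to about the as-dispensed level and unchanged wear. On that assumption, and for losses of 20% to 80% per 30 days, the full-restoration benefit visible at Visit 5 is a between-arm difference of 0.19 to 0.38 of a full coating. These are coating units, not endpoint units.

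The opposite inference is equally unsupported: no significant change in the Boost arm would not by itself show maintenance, because a null result in a small arm may only reflect imprecision. The Boost arm's own Visit 3-to-5 change should count as evidence of neither failure nor success.

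**What to change.** In 1.2 and 25.1, state two contrasts.

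- **Immediate replenishment:** the Visit 3-to-4 change, Boost versus placebo, on measures that can respond in one day: keratograph break-up, acuity and the momentary comfort VAS.
- **Maintenance at Visit 5:** the Boost-minus-placebo difference in Visit 3-to-5 change, or Visit 5 compared between arms with adjustment for Visit 3, reported with a confidence interval. Include the CLDEQ-8, end-of-day comfort and wearing hours.

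Add that the Boost arm's Visit 3-to-5 change will not be interpreted alone. Assign ocular surface staining, also a primary endpoint in 9.1, to one contrast or both.

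This is a change of text only, with no new visits, measurements or subjects. The cost is that the Visit 5 claim becomes maintenance relative to placebo, estimated with limited precision in a 30-subject pilot. Two contrasts over four primary endpoints also add multiplicity, so the plan should say which results are confirmatory and which descriptive.
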